Randomization will be stratified by indication (HABP/VABP/VP versus bacteremia), severity of illness (based on Acute Physiology and Chronic Health Evaluation [APACHE] II [10 to 19 versus 20 to 30], Sequential Organ Failure Assessment [SOFA] [7 to 9 versus ≥10], or quick SOFA [qSOFA] [2 versus 3] score at Screening), and geography (China Mainland versus Rest of World). In the situation where a patient has more than one score reported, the scores will be used in the following order: APACHE, SOFA, and qSOFA.

Enrollment of HABP, VP, and bacteremia patients will be limited to a total of no more than 40% of patients in Part A, regardless of resistance.

- b. Part B will be the open-label, supportive portion of the study that will include patients known to have HABP, VABP, VP, and/or bacteremia infections associated with ABC organisms that are known to be resistant to colistin or polymyxin B, those failing a colistin or polymyxin B regimen prior to study entry or are on acute renal replacement therapy, and patients with infections due to colistin- or polymyxin B-resistant ABC with sources of infection other than HABP, VABP, VP, and/or bacteremia, as detailed in [Section 4.1.3](#).

Any patient who has a qualifying ABC infection and meets study inclusion criteria but has a contraindication to colistin due to underlying conditions, intolerance, or evidence of failing colistin or polymyxin B therapy prior to study entry, and/or has a colistin- or polymyxin B-resistant ABC infection cannot be enrolled in Part A but can be considered for enrollment in Part B (see [Section 4](#) for details).

Patients with ABC infections who are not otherwise eligible for Part A are expected to be enrolled in Part B. Patient enrollment in Part B will continue until Part A enrollment in the CRABC m-MITT Population is complete. In Part B, patients will receive the following treatment:

- Group 3: 1.0 g ETX2514/1.0 g sulbactam IV infused over 3 hours q6h plus 1.0 g imipenem/1.0 g cilastatin IV infused over 1 hour q6h.

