## 4 SELECTION AND WITHDRAWAL OF PATIENTS

### 4.1 Inclusion Criteria

#### 4.1.1 General Inclusion Criteria

Patients who meet all of the following general inclusion criteria, in addition to the specific inclusion criteria listed below for Parts A and B, will be eligible to participate in the study:

1. A signed informed consent form (ICF);

Note: If a study patient is unable to provide informed consent due to their medical condition, the patient's legally authorized representative may consent on behalf of the study patient, or the decision can be made according to the procedure permitted by local law and institutional Standard Operating Procedures in compliance with [Section 6.1](#).

2. Male or female  $\geq 18$  years of age;
3. A confirmed diagnosis of a serious infection and the expectation, in the judgment of the Investigator, that the patient's infection will require treatment with IV antibiotics;
4. A known infection caused by ABC (bacteremia, HABP, VABP, VP, cUTI or AP, or surgical or post-traumatic wound infections) as either a single pathogen or member of a polymicrobial infection based on evidence from culture or, if available, rapid diagnostic test from a sample collected within 72 hours prior to randomization (HABP/VABP/VP patients), AND 1 of the following:
  - a. Has received no more than 48 hours of potentially effective (ie, Gram negative coverage) antimicrobial therapy prior to the first dose of study drug; OR
  - b. Is clinically failing prior treatment regimens (ie, clinical deterioration or failure to improve after at least 48 hours of antibiotic treatment);

Note: Rapid testing of respiratory specimens utilizing BPP technology (see [Section 7.7](#)) should be used to enable early identification of ABC pneumonia. Patients can be randomized based on the results of the BPP rapid test while awaiting results of cultures from the local laboratory. However, if the respiratory sample does not grow ABC in the local microbiology laboratory culture, these patients will be withdrawn from the study drug treatment.

Note: Isolation of ABC from pleural effusion (empyema) is allowed, if concurrent pulmonary infiltrate is confirmed.

5. APACHE II score between 10 and 30, inclusive, OR SOFA score between 7 and 11, inclusive, at the time of diagnosis of infection. Patients who are not being treated in an intensive care unit and cannot have an APACHE II or SOFA score performed should have a qSOFA score  $\geq 2$  for enrollment;

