#### 4.1.3 Part B-Specific Inclusion Criteria

Part B will include patients with the following ABC infections: HABP, VABP, VP, or bacteremia who do not qualify for Part A, and cUTI/AP or surgical or post-traumatic wound infections.

1. Patients with HABP, VABP, VP, or bacteremia should be considered for enrollment in Part B if they meet ANY of the following criteria (*a*, *b*, *c*, OR *d*), in addition to the general inclusion criteria listed in [Section 4.1.1](#):

- a. Has an infection caused by ABC organisms known to be resistant to colistin or polymyxin B (defined as MIC  $\geq 4$  mg/L by a non-agar based method);

For known colistin- or polymyxin B-resistant infections, the following must be satisfied:

- Has a known resistant infection based on evidence from culture and susceptibility testing by a non-agar based method within 72 hours prior to randomization, alone or as a single organism of a polymicrobial infection; AND has received no more than 48 hours of an antimicrobial agent to which the ABC is susceptible prior to the first dose of study drug;

OR

- Has documented clinical evidence of failure (ie, clinical deterioration or failure to improve that is attributable to ABC infection) after at least 48 hours of treatment with colistin or polymyxin B; OR

- b. Has known intolerance to colistin;  
Note: Patients whom the Investigator feels may have a potential intolerance to colistin can be enrolled in Part B on a case-by-case basis after discussion with the Medical Monitor; OR
  - c. Has myasthenia gravis or another neuromuscular syndrome(s) that contraindicates colistin and is not ventilated;  
Note: Ventilated patients with myasthenia gravis or other neuromuscular syndromes where, in the opinion of the Investigator, colistin administration is reasonable are permitted for consideration for the study; OR
  - d. Has acute kidney injury and is receiving renal replacement therapy at study entry;
2. Patients diagnosed with cUTI, AP, or surgical or post-traumatic wound infections may enroll in Part B if they meet the general inclusion criteria listed in [Section 4.1.1](#) as well as either *a*, *b*, *c*, *d*, OR *e* in addition to the indication requirements for *f*:
- a. Has an infection caused by ABC organisms known to be resistant to colistin or polymyxin B (defined as MIC  $\geq$ 4 mg/L by a non-agar based method); OR
  - b. Has known intolerance to colistin;  

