23. Participation in a clinical study involving investigational medication or an investigational device within the last 30 days or 5 half-lives, whichever is longer, prior to Day 1;
24. Any condition that, in the opinion of the Investigator, would compromise the safety of the patient or the quality of the data or require greater than 14 days of treatment with antibiotics;
25. Unable or unwilling, in the opinion of the Investigator, to comply with the protocol;
26. Has previously received ETX2514 in this study; or
27. For Part A only, patients with an infection known to be resistant to colistin or polymyxin B (defined as MIC  $\geq$ 4 mg/L by a non-agar based method), with a known intolerance to colistin, or taking any drug that prevents them from receiving colistin.

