### 5.2 Rationale for Dosing

The doses of ETX2514 and sulbactam to be evaluated in this study have been selected based on Phase 1 and Phase 2 PK, safety, and efficacy data and extensive PK/PD modeling and probability of target attainment against CRABC in the lung. Data from these studies and details of the PK/PD modeling are provided in more detail in the Investigator's Brochure.

ETX2514 1.0 g was generally well tolerated in all of the clinical studies to date. Sulbactam 1.0 g was generally well tolerated in the Phase 2 study. The total daily dose of sulbactam being used in the current study is consistent with the US Product Circular for Unasyn, in which the maximum approved daily dose in patients with normal renal clearance for sulbactam is 4 g, which is equivalent to 1.0 g sulbactam q6h.

The ETX2514SUL regimen of 1.0 g ETX2514/1.0 g sulbactam should be infused over 3 hours q6h given for 7 days to 14 days (28 doses to 56 doses), depending on the clinical response.

Imipenem/cilastatin will be administered as a 1.0 g/1.0 g dose infused over 1 hour q6h given for the same duration as ETX2514SUL or colistin.

Colistin will be administered at a daily dose of 5 mg/kg of colistin base activity (CBA) divided into 2 doses 12 hours apart. Doses will be adjusted to ideal body weight in obese patients. Patients who weigh <60 kg with normal renal function will receive a flat dose of 300 mg CBA or 9 million international unit (MIU)/day. A single loading dose of 2.5 to 5 mg/kg (total dose not exceeding 300 mg CBA or 9 MIU and following local standard of care) given IV over 3 to 6 minutes (or according to standard of care) will be administered on Day 1. Colistin infusions beyond the loading dose on Day 1 will begin 12 hours after the initial loading dose and will be infused over 30 minutes. Details on dosing for those patients who are on colistin prior to randomization into the study can be found in the Pharmacy Manual.

Details of study drug preparation and administration can also be found in the Pharmacy Manual.

No dosing regimen changes, other than those specified in the protocol for renal insufficiency (see [Section 5.3](#)) or for patients on imipenem who develop a seizure that is thought to be directly related to imipenem, can occur without discussion with the Medical Monitor.

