## 7.7 Microbiologic Assessments

To assess the primary indication and follow-up of the primary indication, all specimens will be sent to the local laboratory for culture and susceptibility testing per institutional standards. Pure cultures of isolated pathogens will be shipped from the local laboratory to the central laboratory for confirmation of species identification, susceptibility testing, and possible molecular characterization, as detailed in the Microbiology Laboratory Manual. Definitions of resistance for purposes of this protocol are detailed in [Section 9.1](#) and in the Microbiology Laboratory Manual.

Rapid diagnosis of ABC HABP/VABP/VP will utilize the BPP to detect ABC in respiratory specimens. Details of the test and its use will be included in the Laboratory Manual. The test results will be recorded in the eCRF.

All patients must have a specimen sample from the site of infection (ie, respiratory secretion, blood, urine, or wound) and 2 sets of blood culture samples from 2 separate venipuncture sites collected at Screening. Screening respiratory specimens for patients with suspected HABP/VABP/VP should be subjected to BPP rapid diagnostic testing as detailed above, where available, and submitted to the local microbiology laboratory for culture and susceptibility testing. In these cases, if the local microbiology laboratory culture does not grow ABC, the patient will be withdrawn from the study drug treatment.

If the screening sample for culture that is growing ABC is taken per standard of care before the patient or patient's legally authorized representative signs informed consent, that isolate may be used for baseline eligibility and sent to the central laboratory once consent is obtained, as long as the sample was collected within 72 hours prior to randomization. Additional samples for baseline culture should be collected again within 24 hours prior to randomization, at the time points specified in the Schedule of Procedures ([Appendix A](#)), and if clinically indicated. Patients who are failing their current treatment as evidenced by worsening clinical condition may enroll in the study, provided they meet all other requisites. However, additional samples must be taken from the site of infection within 24 hours prior to randomization and sent to the local laboratory for culture.

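### Protocol 3.1 bars patients already failing colistin or polymyxin B from Part A, but the numbered eligibility criteria do not carry that bar

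*Protocol*

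**What the plan says.** **The bar.** Protocol 3.1 lists several kinds of patient, among them those with "evidence of failing colistin or polymyxin B therapy prior to study entry", and says that they "cannot be enrolled in Part A but can be considered for enrollment in Part B". It refers to Section 4 for details. The synopsis (Study Design and Duration) and SAP 3.1 repeat the rule.

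**The numbered criteria.**
- Exclusion 27 (Protocol 4.2 and synopsis) reads "For Part A only, patients with an infection known to be resistant to colistin or polymyxin B", then adds known colistin intolerance and use of a medicine that rules colistin out. Clinical failure on a polymyxin is not listed.
- General inclusion 4b, which applies to both parts, admits a patient who "Is clinically failing prior treatment regimens (ie, clinical deterioration or failure to improve after at least 48 hours of antibiotic treatment". It makes no exception for polymyxins.
- Protocol 7.7 says: "Patients who are failing their current treatment as evidenced by worsening clinical condition may enroll in the study". Again there is no exception. The same section allows Part A enrollment before the resistance profile is established.
- Part B criterion 1a (Protocol 4.1.3) offers the route "Has documented clinical evidence of failure (ie, clinical deterioration or failure to improve that is attributable to ABC infection" after at least 48 hours of a polymyxin, but as a bullet under the conditions for known resistant infections. For urinary and wound infections, failure is a free-standing criterion (2e).

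**The concern.** Site staff screen against the numbered lists. A pneumonia or bacteremia patient who is deteriorating on colistin, and whose isolate is susceptible or not yet tested, meets inclusion 4b and is not caught by exclusion 27. Read literally, that patient may also miss Part B criterion 1a. This is the reverse of what Section 3.1 intends. Two sites reading the same protocol could act differently, and one of them could randomize the patient to the drug already being failed.

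At stake are, first, patient safety and a consistent definition of the pivotal population. Second, if such patients die more often on continued colistin than after a switch to ETX2514SUL, the control rate in the primary comparison rises and the 20-point margin becomes easier to meet.

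**Working it through.** **1. Do the later rules remove these patients?**
- Protocol 9.1 and SAP 8.4 drop isolates that the central laboratory finds resistant to colistin or ETX2514SUL from the CRABC m-MITT Population. A clinical failure with a susceptible isolate stays in.
- Protocol 7.7 transfers or withdraws patients with locally detected colistin resistance. It does not act on clinical failure before entry.
- Stopping study drug does not remove a patient from the primary analysis (Protocol 9.2.2.1).
- None of the sensitivity analyses in SAP 9.3.1 or subgroups in SAP 9.3.4 isolates prior polymyxin failure. The nearest subgroups are any prior antibiotic, and any within 24 hours, yes or no.

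The gap therefore remains for failures whose isolate is not shown to be resistant.

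**2. Reproduce the plan's sample size.** Inputs from Protocol 9.2.5: mortality 41% (control) and 36% (test), margin 20 points, two-sided 95% CI, 80% power, 120 patients, hence 60 per arm.

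SE = √[(0.36×0.64 + 0.41×0.59)/60] = √(0.4723/60) = 0.0887.

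Power = Φ[(0.20 + 0.05)/0.0887 − 1.96] = 80.5%. The stated figure is reproduced.

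SAP 9.3.1 uses a continuity-corrected interval. Subtracting 1/60 from the numerator gives 74.9%. That shortfall is a separate matter.

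**3. Size of the possible shift.** Let f be the share of polymyxin-failing patients in each arm, and d their excess mortality in the control arm over what would preserve the planned difference. The control rate becomes 41% + f×d. The documents give neither f nor d. Assumed range:
- lowest: 5% × 10 points = 0.5 points
- middle: 10% × 15 points = 1.5 points
- highest: 15% × 20 points = 3.0 points

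Power is for 36% on test. The false non-inferiority rate takes 61% on test, a true difference of +20 points from the planned 41%. Corrected false rates come from exact binomial enumeration; the other columns use the normal approximation.

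| Control shift | Power, uncorrected | Power, corrected | False NI, uncorrected | False NI, corrected |
|---|---|---|---|---|
| 0 | 80.5% | 74.9% | 2.5% | 1.7% |
| 0.5 | 81.9% | 76.5% | 2.8% | 1.9% |
| 1.5 | 84.6% | 79.7% | 3.7% | 2.5% |
| 3.0 | 88.1% | 84.0% | 5.2% | 3.7% |

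**4. Check without a differential effect.** If 20% of each arm are such patients and their mortality is 20 points higher in both arms, the rates become 40% and 45%. Power is 79.2% and the false non-inferiority rate stays at 2.5% (uncorrected). Non-inferiority is not eased.

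**The case against.** The strongest reply is that the rule already exists and binds. Section 3.1, the synopsis and the SAP state it, and the descriptions of Part B name patients failing a polymyxin regimen as Part B patients. Randomizing one in Part A would contradict explicit text. Inclusion 4b is a general criterion: it can admit failures of other regimens to Part A and polymyxin failures to Part B, so taken alone it does not conflict with 3.1. The investigator may also decline a patient under inclusion 6 or exclusion 24.

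This narrows the point without removing it. Section 3.1 sends the reader to Section 4, where the bar is missing, and criterion 1a does not clearly receive the patients whom 3.1 redirects. Investigator discretion is not a rule.

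Three stronger readings are tempting and are not supported:
- **That non-inferiority is necessarily eased.** Randomization places these patients in both arms. A purely prognostic effect does not help the test drug (step 4), and the documents give no figure for a differential one.
- **That Section 5.2 expects failing patients.** It mentions "those patients who are on colistin prior to randomization into the study". Being on colistin is not failing it, and inclusion 4a allows up to 48 hours of prior effective therapy.
- **That acute renal replacement therapy at entry is part of the same contradiction.** It is a Part B criterion and is not a Part A exclusion, but the barring sentence in 3.1 does not name it, and Table 1 gives colistin regimens for dialysis. At most it needs a separate clarification.

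**Conclusion.** The inconsistency stands on the text alone: the design sections bar a group that the numbered criteria let through. It bears on who may be randomized in the pivotal part and on patient safety, and it should be corrected whatever its statistical effect.

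The effect on the primary result is conditional and probably modest. It requires that polymyxin-failing patients actually enter Part A and that they do worse on continued colistin than on ETX2514SUL. Under the assumed 5-15% and 10-20 points, control mortality rises 0.5-3.0 points. With the SAP's own interval, the false non-inferiority rate passes the nominal 2.5% only in the upper half of that range and reaches 3.7% at the top. If sites already follow Section 3.1, the share is close to zero and so is the effect.

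**What to change.** 1. Reconcile Protocol 3.1, the synopsis and SAP 3.1 with exclusion 27, general inclusion 4b, Section 7.7 and Part B criterion 1a, so that the Part A and Part B criteria state one rule on prior polymyxin failure. Which rule is right is for the sponsor to settle.
2. In the SAP, define a baseline flag for prior polymyxin failure and repeat the primary analysis without flagged patients. Protocol 5.6.4 already collects antibiotics from the 14 days before first dose, with start and stop times and indication. These data show exposure and its duration, not failure, so the flag should also use whether the patient qualified under 4a or 4b. The documents do not say whether the eCRF records that; if it does not, add the item.
3. Clarify separately whether acute renal replacement therapy at entry is compatible with Part A.

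The cost is a few lines of eligibility text, one derived variable and one sensitivity analysis. At the assumed 5-15%, that analysis would drop 6 to 18 of the 120 patients, so it should be read for consistency of the estimate and not as a second powered test. If the reconciled rule keeps these patients out, enrollment changes only at sites that would otherwise have randomized them.

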4.1.2 Part A-Specific Inclusion Criteria

In addition to those general inclusion criteria listed in [Section 4.1.1](#), patients may enroll in Part A if they meet the criteria below. All patients must be categorized in 1 infection type that is judged to be the primary infection by the Investigator:

1. Diagnosed with HABP, VABP, VP, and/or bacteremia, defined as:

HABP With ABC in Sputum/Respiratory Sample		
All of the following:	AND signs or symptoms evidenced by at least 2 of the following:	AND at least 1 of the following:

 
Onset of symptoms >48 hours after admission or ≤7 days after discharge from an inpatient acute or chronic care facility (eg, LTAC, rehabilitation center, hospital, or skilled nursing home); OR
 
Admission from LTAC or rehabilitation center, or admission from home <7 days after discharge from an LTAC or rehabilitation center; AND
 
New or evolving infiltrate on chest X-ray, MRI, CT scan, or ultrasound obtained within 48 hours prior to randomization. Note: If an ultrasound is performed, a confirmatory X-ray or CT scan should be performed within 24 hours.
 
	
 
A new onset of cough (or worsening of baseline cough);
 
Auscultatory findings consistent with pneumonia/pulmonary consolidation (eg, rales, dullness on percussion, bronchial breath sounds, or egophony);
 
Dyspnea, tachypnea, or respiratory rate >25 breaths/minute; OR
 
Hypoxemia (oxygen saturation <90% or pO2 <60 mmHg while breathing room air, or worsening of the oxygen saturation/ FiO2); OR the following ALONE:
 
New onset need for mechanical ventilation.
 
	
 
Fever [1] (oral or tympanic temperature ≥38°C [≥100.4°F] or rectal/core temperature ≥38.3°C [≥100.9°F]) OR hypothermia (rectal/core temperature <35°C [<95°F]);
 
Elevated total peripheral WBC count (>10,000/mm^3);
 
>15% immature neutrophils (bands) regardless of total peripheral WBC count; OR
 
Leukopenia (total WBC count <4500/mm^3).
 

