Note: Patients who can maintain MAP  $\geq 60$  mmHg on a reasonable dose of pressors or are weaning off of pressors may be considered. Patients who require more than the maximal dose of 2 vasopressors to maintain MAP  $\geq 60$  mmHg are ineligible. If vasopressors are weaned to below these levels, patient enrollment can be reconsidered.

8. For patients to be enrolled with the primary indication of HABP, VABP, or VP, any of the following conditions:
  - a. Diagnosis of ventilator-associated tracheobronchitis; or
  - b. Inability to provide proper respiratory specimens for culture. Respiratory samples from expectorated or induced sputum should show  $< 10$  squamous epithelial cells and  $> 25$  polymorphonuclear neutrophils per  $100\times$  field;
9. For patients to be enrolled with the primary indication of cUTI or AP, any of the following urologic conditions:
  - a. Likely to receive ongoing antibacterial drug prophylaxis after treatment of cUTI (eg, patients with vesico-uretal reflux);
  - b. Suspected or confirmed prostatitis;
  - c. Requirement for bladder irrigation with antibiotics or for antibiotics to be administered directly via urinary catheter;
  - d. Previous or planned cystectomy or ileal loop surgery;

- e. Uncomplicated urinary tract infection (eg, female patients with urinary frequency, urgency, or pain or discomfort without systemic symptoms or signs of infection);
  - f. Complete, permanent obstruction of the urinary tract;
  - g. Suspected or confirmed perinephric or renal corticomedullary abscess;
  - h. Polycystic kidney disease; or
  - i. Any recent history of trauma to the pelvis or urinary tract;
10. Pregnant or breastfeeding women;
11. APACHE II score >30 and SOFA score >11 at the time of diagnosis of infection;
- Note: A qSOFA score must be calculated for all patients without an APACHE II score. Glasgow coma score for APACHE II calculation should be the best response prior to initiation of sedation/neuromuscular blockade, even if sedation has been in use for >24 hours.
12. Receiving peritoneal dialysis;

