**Table 2. Definition of RIFLE Criteria**

Term	Definition
Risk (R)	Increased creatinine level 1.5× or GFR decrease >25%
Injury (I)	Increased creatinine level 2× or GFR decrease >50%
Failure (F)	Increased creatinine level 3×, GFR decrease >75%, or creatinine level ≥4 mg/dL
Loss (L)	Persistent acute renal failure or complete loss of function for >4 weeks
ESKD (E)	ESKD for >3 months

ESKD = end-stage kidney disease; GFR = glomerular filtration rate; RIFLE = Risk–Injury–Failure–Loss–End-stage renal disease.

The number and percentage of patients reporting adverse events of special interest will be summarized by each category and treatment group in Part A in the Safety and CE Populations. In addition, proportion of patients with nephrotoxicity will be compared between the investigational and control groups using Chi-square test. The Chronic hemodialysis patients will not be included in the nephrotoxicity analysis.

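### No numbered criterion keeps patients on acute renal replacement therapy out of Part A, and the SAP would leave any who enter in the primary RIFLE comparison

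*Protocol*

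**What the plan says.** **Where acute-RRT patients are meant to go.** Protocol Section 3.1 describes Part B as including, among others, "those failing a colistin or polymyxin B regimen prior to study entry or are on acute renal replacement therapy". Section 4.1.3, criterion 1d, makes this a listed route into Part B for pneumonia and bacteremia: "Has acute kidney injury and is receiving renal replacement therapy at study entry". The lead-in to that section describes these Part B patients as those with "HABP, VABP, VP, or bacteremia who do not qualify for Part A".

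**What the Part A criteria say.** The Part A-specific inclusion criterion (Section 4.1.2) is by infection type: "Diagnosed with HABP, VABP, VP, and/or bacteremia, defined as". It has no renal condition. In Section 4.2 the only dialysis exclusion is number 12, "Receiving peritoneal dialysis". The only exclusion specific to Part A is number 27, which covers known colistin or polymyxin B resistance and patients "with a known intolerance to colistin, or taking any drug that prevents them from receiving colistin". Section 3.1 separately bars from Part A a patient who "has a contraindication to colistin due to underlying conditions, intolerance, or evidence of failing colistin or polymyxin B therapy prior to study entry", or who has a resistant isolate.

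**What the SAP does.** Comparing RIFLE nephrotoxicity in Part A is one of two primary objectives. SAP 9.4.1 tests it with a chi-square test and states: "The Chronic hemodialysis patients will not be included in the nephrotoxicity analysis". SAP 9.1.3 takes baseline as the last value before the first dose, with no rule for values obtained on RRT.

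**The concern.** RIFLE Risk and Injury, and most of Failure, are defined by change in creatinine or GFR. For a patient already on RRT, creatinine may move because RRT is continued, changed or stopped, whichever study drug is given. Failure also has an absolute limb, creatinine of 4 mg/dL or more, with no rise required, so a patient with acute kidney injury could count as an event from a value present at entry. Either way the RIFLE category says little about the study drug.

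The SAP already leaves chronic hemodialysis patients out of this comparison. Acute RRT raises a similar difficulty for a creatinine-based measure, yet the SAP is silent on it. At stake is the clarity of a primary-objective comparison, and whether a site working down the numbered list would place such a patient as Section 3.1 intends.

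**Working it through.** **1. Does any rule keep an acute-RRT patient out of Part A?**

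| Source | Names acute RRT? |
|---|---|
| Part A inclusion (4.1.2) | No; infection type only |
| Exclusion 12 (4.2) | No; peritoneal dialysis only |
| Exclusion 27 (4.2) | No; resistance, intolerance, interfering drug |
| Section 3.1, bar from Part A | No; contraindication, intolerance, failure, resistance |
| Section 3.1, description of Part B | Yes, as a Part B group |
| Part B criterion 1d (4.1.3) | Yes, as a Part B route |

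The intended placement is stated, but only on the Part B side. Exclusion 24 lets an investigator exclude on judgment, which is not a rule about RRT. A patient already randomized could not be moved on this ground, because Section 3.1 allows transfer to Part B only for colistin or polymyxin B resistance.

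**2. Would the analysis remove such a patient?** No. The Safety Population is every treated patient, and the Clinical Evaluable definition has no RRT condition. SAP 9.4.1 drops only chronic hemodialysis. RRT at entry is also absent from the baseline table (SAP 9.2.3) and the subgroup list (SAP 9.3.4), so no planned summary would show how many there were.

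**3. The plan's own figures.** The nephrotoxicity comparison has no stated sample size or power. The only sample size is for mortality, and it reproduces. With 41% versus 36%, a 20-point margin and 60 per arm, SE = √[(0.41×0.59 + 0.36×0.64)/60] = 0.0887, and power = Φ(0.25/0.0887 − 1.96) = 80.5%. Enrollment is 120/0.60 = 200, or about 100 per arm. Only the 200 is used below.

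**4. One patient, on assumed values.** Pre-dose creatinine is 1.3 mg/dL on continuous RRT; RRT stops and creatinine settles at 2.8 mg/dL. The ratio is 2.8/1.3 = 2.15, which is RIFLE Injury (2×) with no drug effect.

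**5. Size, on assumed values.** Let a share *f* of each arm be on acute RRT at entry, with the same RIFLE rate *q* in both arms. Let the other patients have rates *p*₁ (ETX2514SUL) and *p*₂ (colistin). Then

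observed difference = (1−f)p₂ + fq − [(1−f)p₁ + fq] = (1−f)(p₂ − p₁).

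For a true difference of 20 points:

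- f = 2% of 200 = 4 patients: 0.98 × 20 = 19.6 points
- f = 10% of 200 = 20 patients: 0.90 × 20 = 18 points

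For power, take p₁ = 20%, p₂ = 40%, n = 100 per arm, two-sided 5%, and q from 30% to 90%:

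power = Φ{[Δ − 1.96√(2p̄(1−p̄)/n)] / √[(p₁(1−p₁) + p₂(1−p₂))/n]},

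where Δ is the observed difference, p̄ is the mean of the two rates, and p₁ and p₂ are replaced by the mixed rates when RRT patients are kept. With no such patients, power is 88%.

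| f | Power, kept in | Power, removed |
|---|---|---|
| 5% | 84-82% | 86% |
| 10% | 80-76% | 84% |

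**6. Chance imbalance, same assumed rates.** With shares of 5% and 10% in the two arms and q = 90%:

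- more in the colistin arm: (0.90×0.40 + 0.10×0.90) − (0.95×0.20 + 0.05×0.90) = 0.450 − 0.235 = 21.5 points
- more in the ETX2514SUL arm: (0.95×0.40 + 0.05×0.90) − (0.90×0.20 + 0.10×0.90) = 0.425 − 0.270 = 15.5 points

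The shift can go either way.

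**The case against.** The strongest reply is that placement is already settled. Section 3.1 puts acute-RRT patients in Part B, and the synopsis and SAP repeat it. The lead-in to Section 4.1.3 is most naturally read as saying that the patients listed in criteria a to d are those who do not qualify for Part A. Exclusion 27 was never the whole bar either: it omits failure on colistin and neuromuscular contraindications, which Section 3.1's bar covers by naming colistin failure and contraindications due to underlying conditions. This stands as evidence of intent. It does not close the gap, because that sentence in Section 3.1 does not reach RRT.

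A reader might infer more than the documents support:

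- **That Table 1 shows acute-RRT patients may enter Part A.** Its colistin entries for hemodialysis and continuous RRT can serve patients who start RRT on study, or chronic hemodialysis patients.
- **That placement is left to site preference, or that the SAP assumes no acute-RRT patient is in Part A.** Neither document says so; the SAP gives no reason for naming only chronic hemodialysis.
- **That baselines are lowered by dialysis and the comparison is biased.** The documents do not discuss creatinine on RRT. Allocation within Part A is randomized, so noise or dilution is more likely than systematic bias toward one arm.

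It is also fair to say that if the eligibility text is reconciled to keep these patients out of Part A, the SAP change affects only misenrolled patients. An analysis with and without them is a defensible alternative to omission, and the fix therefore includes both.

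**Conclusion.** The point holds as a gap in enforcement and in analysis handling. The protocol states where acute-RRT patients belong, no Part A criterion carries that out, and the SAP would keep any who are randomized in a primary-objective comparison that cannot be interpreted for them. The textual gap is clear.

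Its effect is uncertain and probably modest. The documents give no prevalence, and the direction of any bias is unknown. The loss of 0.4 to 2 points from a 20-point difference rests on an assumed 2-10% share, an assumed 20-point effect, and equal shares and equal RIFLE rates for RRT patients in both arms. The power figures also rest on assumed rates of 20% and 40%. Shares at that level would require sites to depart repeatedly from Section 3.1. The gap is worth closing before database lock, but it does not undermine the comparison, and the mortality endpoint is not in question here.

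**What to change.** 1. **Protocol.** Reconcile Section 3.1, Part B criterion 1d and exclusion 27 so that a patient on acute RRT at study entry qualifies for exactly one part. The sponsor should decide which.
2. **SAP 9.4.1.** Replace chronic hemodialysis patients, as the group left out of the RIFLE comparison, with *patients receiving any renal replacement therapy (acute or chronic) before the first dose of study drug*. List these patients separately by arm, and give a supportive analysis that includes the acute-RRT patients.

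The second change is defined by pre-dose status, so it does not condition on outcome, and it is valid however the first is resolved. RRT status at entry is already needed to apply criterion 1d and to use Table 1. The cost is one eligibility clause, one SAP phrase, one listing and one supportive table, and a few patients leave the nephrotoxicity denominator.
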